1.6.2 Potential benefits

This research study may change how patients are treated with simple hand/upper extremity inflammatory disorders.

2 Study Objectives

The primary objective of this study is to compare local corticosteroid hand and elbow injections to ketorolac to determine if there is an equal or better reduction of symptoms for common orthopaedic upper extremity disorders including: De Quervain's tenosynovitis, trigger fingers, and tennis elbow (lateral epicondylitis).

3 Study Design

3.1 General Design

This study will be a double-blinded prospective randomized controlled trial comparing the effects of dexamethasone (standard of care) and ketorolac in hand and upper extremity soft tissue disorders.

3.2 Primary Study Endpoints

The primary endpoint will be functional outcome scores at various follow-up time points using the quickDASH and EQ-5D questionnaire as well as a pain visual analog scale. The primary endpoint for the study would be resolution of symptoms or surgical intervention.

Primary endpoints will depend on the diagnosis of the patient. The following details what will be assessed at each follow-up visit after the initial injection:

- 1) Trigger finger group primary endpoint measures include the resolution of objective triggering and resolution of tenderness at the A1 pulley at subsequent follow-up visits. In addition, patients will be graded based on the Quinnell system to monitor for improvement: 0-normal movement of finger; 1-uneven movement; 2-active correctible locking of digit; 3-passively correctible locking; 4-fixed deformity (15). Patients will complete the quickDASH and EQ-5D questionnaires as well as a pain visual analog scale at each follow-up visit (27).
- 2) De Quervain's tenosynovitis group primary endpoint measures will include objective physical exam findings for the resolution of pain/tenderness over the 1st dorsal extensor compartment and the resolution of pain elicited during the Finkelstein test. In addition, patients will complete the quickDASH and EQ-5D questionnaires as well as a pain visual analog scale at each follow-up visit.
- 3) Lateral epicondylitis of the elbow group primary endpoint measures include the resolution of lateral elbow pain/tenderness over the extensor origin and the resolution of pain at the lateral epicondyle with resisted wrist extension during follow-up examinations. Patient grip strength will also be measured in this cohort using a hand dynamometer. Grip strength will be measured at each follow-up and the average of three tests with 20 second rests in between will be recorded. The contralateral side will also be measured for comparison. Lastly, patients will complete the quickDASH and EQ-5D questionnaires as well as a pain visual analog scale at each follow-up visit.

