3.3 Secondary Study Endpoints

Secondary outcome measures include objective physical exam findings (clinical grading/classification systems), and grip/pinch strength using dynamometers.

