3.4 Primary Safety Endpoints

Patients will follow-up after the first injection at 4-weeks, 8-weeks, 12-weeks, and 6 months post injection. During follow-up appointments patients in this study will be monitored based on history and physical exam for any side-effects associated with the administration of local soft tissue injections of dexamethasone or ketorolac.

Patients can withdraw from the study at any time if they wish. Patients whose symptoms do not improve and are candidates for surgery can withdraw from the study and have surgery to correct their specific pathology (secondary endpoint). Patients enrolled in the study will be counseled regarding the likelihood of

the injections working and will be given the opportunity for a second injection at 4 weeks from the time of the first injection if no significant symptoms have resolved. Ultimately it will be up to the patient whether they chose another injection or if they want to resort to a surgical intervention.

Patients who receive ketorolac by randomization as the therapeutic option will have an expected failure rate of approximately 30-50% based on clinical experience and literature review that shows the failure rate of dexamethasone (standard of care) on trigger fingers. The study population will be statistically analyzed biannually to determine if there is a significant difference in the rate of failures between the two groups, however a sizeable study population needs to be established before these conclusions can be drawn. If the rate of failure proves to be statistically significant between the ketorolac and dexamethasone group then the study will have to be ethically abandoned. This determination needs to take into consideration the pretreatment symptoms of the patient since patients who begin treatment with a severe trigger finger (quinnell score=4) have a different prognosis compared to patients who begin with a mild trigger finger (quinnell score=1).

4 Subject Selection and Withdrawal

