4.4 Subject Withdrawal

Patients can withdraw from the study at any time if they wish. Patients whose symptoms do not improve and are candidates for surgery can withdraw from the study and have surgery to correct their specific pathology (secondary endpoint). Patients enrolled in the study will be counseled regarding the likelihood of the injections working and will be given the opportunity for a second injection at 4 weeks from the time of the first injection if no significant symptoms have resolved. Ultimately it will be up to the patient whether they chose another injection or if they want to resort to a surgical intervention.

If patients experience adverse events they will be counseled regarding treatment alternatives for their pathology and any complications from the injection/medications will be treated appropriately. Because the study consists of a single injection at time point zero followed by serial examinations and completion of functional outcome surveys there is no need to stop treatment and withdraw patients from the study despite having an adverse event. The patient will simply not receive any more injections.

5 Study Drugs

5.1 **Ketorolac** (Investigational Agent)

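### The primary endpoint is named in conflicting ways, the failure comparison that can end the study has no operational definition in the documents supplied, and no rule covers operated patients' scores

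*Combined protocol and SAP*

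**What the plan says.** Section 3.2 uses the word primary in three ways.

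- Scores: "The primary endpoint will be functional outcome scores at various follow-up time points using the quickDASH and EQ-5D questionnaire", together with a pain visual analogue scale.
- An outcome statement: "The primary endpoint for the study would be resolution of symptoms or surgical intervention". Sections 5.1.2 and 5.4 repeat it.
- Examination findings: "Primary endpoints will depend on the diagnosis of the patient". A list follows for trigger finger, De Quervain's tenosynovitis and lateral epicondylitis.

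Other sections label the same items differently.

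- Section 3.3: "Secondary outcome measures include objective physical exam findings".
- Section 7.2 puts quickDASH and EQ-5D in the primary analysis, and examination findings and symptom resolution in the secondary analysis. It does not mention the pain scale.
- Section 10.1 calls resolution primary and surgery secondary. Sections 3.4 and 4.4 also call surgery secondary.
- Section 7.1 bases the sample size on mean DASH, whereas the instrument collected is quickDASH.

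Section 3.4 plans a twice-yearly check for a "significant difference in the rate of failures between the two groups" and says that if one is found "the study will have to be ethically abandoned". It gives an "expected failure rate of approximately 30-50% based on clinical experience and literature review that shows the failure rate of dexamethasone" in trigger finger, but no event and no visit. On surgery, 4.4 says: "Patients whose symptoms do not improve and are candidates for surgery can withdraw from the study and have surgery to correct their specific pathology".

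**The concern.** Three gaps follow, and all concern what is measured, when and in whom.

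First, the plan does not fix one result in advance as the test of the trial. A score at any of four visits, a resolution rate or an examination finding could each be presented as primary once the data are known.

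Second, the comparison that can end the study changes meaning with the definition of failure. Sections 3.4 and 4.4 leave surgery to the patient's choice. If failure means surgery only, the comparison partly measures willingness to be operated on. Section 10.1 offers only resolution or surgery, so a patient who still has symptoms but is not operated on has no category. Nor is it stated whether a second injection counts.

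Third, leaving the study for surgery is linked to outcome. If only retained patients' scores are compared, the worst outcomes are removed, possibly to a different extent in each group.

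**Working it through.** **1. The plan's own figure.** Section 7.1 gives a difference of 10, SD 25, alpha 0.05 and power 80% (two-sided assumed). Per drug, n = 2 × (1.960 + 0.842)² × 25² / 10² = 98.1, so 99 per drug and 198 in total. The t-test version gives 99.08, so 100 per drug and 200 in total. The stated 200 is reproduced. It is a comparison of mean scores between two drugs within one diagnosis, so of the candidates in 3.2 only a mean functional score is powered.

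**2. Labels side by side.**

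| Item | Called primary | Called secondary |
|---|---|---|
| quickDASH, EQ-5D | 3.2, 7.2 | – |
| Pain scale | 3.2 | – (absent from 7.2) |
| Examination findings | 3.2 | 3.3, 7.2 |
| Resolution | 3.2, 5.1.2, 5.4 (joined with surgery); 10.1 | 7.2 |
| Surgery | 3.2, 5.1.2, 5.4 (joined with resolution) | 3.4, 4.4, 10.1 |

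**3. Multiplicity.** Section 7.2 names two scores, four follow-up visits and a threshold of 0.05, but no between-drug test. Suppose each score were compared between drugs at each visit, giving 8 tests. If independent, the chance of at least one false positive is 1 − 0.95⁸ = 0.337. By simulation with a common correlation of 0.5 it is 0.250, and with 0.7 it is 0.191. The range is therefore about 19-34% per diagnosis.

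**4. Definition of failure.** All rates here are assumptions. Let f be the share failing and s the share of failures operated on, with 100 per drug and one crude two-sided pooled z test at 0.05. Power is approximately Φ((d − 1.96 × SE₀) / SE₁), where d is the difference, SE₀ = √(2p̄(1−p̄)/n) and SE₁ = √((p₁q₁ + p₂q₂)/n).

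- Equal f = 0.40, with s = 0.4 vs 0.6. Under surgery only, the rates are 0.40 × 0.4 = 0.16 and 0.40 × 0.6 = 0.24. SE₀ = 0.0566 and SE₁ = 0.0563, so Φ((0.08 − 0.1109)/0.0563) = 0.29. Under surgery or non-resolution the rates are equal and the test rejects 5% of the time.
- f = 0.30 vs 0.50, with s = 0.5 in both. Under surgery or non-resolution, SE₀ = 0.0693 and SE₁ = 0.0678, so Φ((0.20 − 0.1358)/0.0678) = 0.83. Under surgery only (0.15 vs 0.25), SE₀ = 0.0566 and SE₁ = 0.0561, so Φ((0.10 − 0.1109)/0.0561) = 0.42.

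**5. Retained-only scores.** Assume a mean of 20 in successes and 50 in failures. The retained mean is (20(1−f) + 50f(1−s)) / ((1−f) + f(1−s)), where s is now the share of failures leaving.

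- Equal f = 0.40, with s = 0.4 vs 0.6: (12 + 12)/0.84 = 28.6 vs (12 + 8)/0.76 = 26.3. The true mean is 20 × 0.6 + 50 × 0.4 = 32 in both groups, so a difference of 2.3 appears where there is none.
- f = 0.30 vs 0.50, with s = 0.5 in both: 21.5/0.85 = 25.3 vs 22.5/0.75 = 30.0, a difference of 4.7. The true difference is 35 − 29 = 6.0.

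**The case against.** Several points on the other side stand.

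- Section 7.2 does rank outcomes: quickDASH and EQ-5D first; examination findings, resolution and strength after. It would be wrong to say that the plan has no order. What is missing is one instrument, one visit and a stated between-drug test.
- The diagnosis-specific findings in 3.2 are mostly resolutions of particular signs. They may be the per-diagnosis meaning of symptom resolution, which would leave two competing primaries. The conflict with 3.3, 7.2 and 10.1 remains.
- Section 10.1 gives a loose sense of failure, namely surgery after an injection that did not relieve symptoms. Sections 8.4 and 10.1 also point to a full Data and Safety Monitoring Plan, which may define it. A reader might infer that failure is defined nowhere; the documents supplied cannot show that.
- The model in step 4 is simpler than 3.4, which looks repeatedly and says that pretreatment severity must be considered. It also takes one diagnosis at a time, and 3.4 does not say whether diagnoses are pooled. At about 300 per drug, surgery only at 15% vs 25% would have about 87% power rather than 42%: SE₀ = 0.0327, SE₁ = 0.0324, Φ((0.10 − 0.0640)/0.0324) = 0.87. Pooling does not cure the false signal: at 16% vs 24%, SE₁ = 0.0325 and Φ((0.08 − 0.0640)/0.0325) = 0.69.
- The bias in step 5 depends on assumed rates of leaving and ignores visit timing. Its size and direction in this trial cannot be known in advance.

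A reader might also infer that the trial intends to count a cure and an operation as the same event. The documents do not support this: 5.1.2 lists them as separate outcomes, 10.1 sets them as alternatives, and 7.2 plans no such analysis. The sentence is faulty drafting, repeated three times, and needs no power calculation.

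The pilot label does not remove the point, since the synopsis describes a Phase 3 trial of 780 subjects and 7.1 and 7.2 set formal power and a significance threshold.

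**Conclusion.** The concern holds and should be fixed before analysis. The conflict of labels is shown by the text alone and rests on no assumption. Its cost, if 7.2 is carried out as between-drug tests of two scores at four visits, is a false-positive chance of about 19-34% per diagnosis for correlations of 0.7 to 0.

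The failure comparison has no operational definition in the documents supplied: no event, no visit, and no place for second injections or for patients unresolved without surgery. The 29% rejection rate with equal true failure shows that the definition matters. It is conditional on 40% failure, 40% vs 60% of failures operated on, 100 per drug and one crude test. The 30-50% in 3.4 is a single expectation for ketorolac borrowed from dexamethasone, not a contrast between drugs, so no document figure predicts the actual effect.

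The absence of a rule for operated patients' scores is also clear. Section 10.1 keeps monitoring patients who drop out, so their data need not be lost, but no section says how those data enter the analysis. A retained-only comparison can therefore be biased; the documents do not allow its direction to be stated.

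**What to change.** 1. Name one primary endpoint: quickDASH at one stated scheduled visit, compared between drugs within each diagnosis, which matches how 7.1 sizes the trial. Name the same instrument in 7.1.
2. Make the other scores and visits, examination findings, resolution and surgery secondary. Delete the sentence that joins resolution and surgery in 3.2, 5.1.2 and 5.4, and align the labels in 3.3, 3.4, 4.4, 7.2 and 10.1.
3. For the comparison in 3.4, state one failure definition at a stated visit that classifies every patient, including those unresolved without surgery and those given a second injection. It must agree with the Data and Safety Monitoring Plan.
4. Analyse as randomised, and keep collecting scheduled scores after surgery or withdrawal where the patient agrees. Pre-specify one rule for operated patients' scores, with the alternative as a sensitivity analysis. If that rule changes the variable analysed, recheck the difference and SD assumed in 7.1.

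Cost: mainly protocol wording, plus a few more questionnaires from operated or withdrawn patients. The demoted endpoints become supportive only. The rule for operated patients is a convention that has to be justified. Whether the sample size is affected depends on the recheck in item 4.

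As a separate item, 1.6.1 has patients with an adverse event withdrawn, while 4.4 says that withdrawal is not needed. The two sections must be reconciled; which is right is not a statistical question.

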3.3 Secondary Study Endpoints

Secondary outcome measures include objective physical exam findings (clinical grading/classification systems), and grip/pinch strength using dynamometers.

3.4 Primary Safety Endpoints

Patients will follow-up after the first injection at 4-weeks, 8-weeks, 12-weeks, and 6 months post injection. During follow-up appointments patients in this study will be monitored based on history and physical exam for any side-effects associated with the administration of local soft tissue injections of dexamethasone or ketorolac.

Patients can withdraw from the study at any time if they wish. Patients whose symptoms do not improve and are candidates for surgery can withdraw from the study and have surgery to correct their specific pathology (secondary endpoint). Patients enrolled in the study will be counseled regarding the likelihood of

the injections working and will be given the opportunity for a second injection at 4 weeks from the time of the first injection if no significant symptoms have resolved. Ultimately it will be up to the patient whether they chose another injection or if they want to resort to a surgical intervention.

Patients who receive ketorolac by randomization as the therapeutic option will have an expected failure rate of approximately 30-50% based on clinical experience and literature review that shows the failure rate of dexamethasone (standard of care) on trigger fingers. The study population will be statistically analyzed biannually to determine if there is a significant difference in the rate of failures between the two groups, however a sizeable study population needs to be established before these conclusions can be drawn. If the rate of failure proves to be statistically significant between the ketorolac and dexamethasone group then the study will have to be ethically abandoned. This determination needs to take into consideration the pretreatment symptoms of the patient since patients who begin treatment with a severe trigger finger (quinnell score=4) have a different prognosis compared to patients who begin with a mild trigger finger (quinnell score=1).

4 Subject Selection and Withdrawal

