10.1 Study Monitoring

For full details on study data and safety monitoring, see the accompanying Data and Safety Monitoring Plan for this study. The responsibility for gathering the data will rest with the individual investigators/health care providers that are directly treating the patients (either at the NYU HJD hand clinic on 23rd street or in the private office of hand attending). Individuals treating patients will be informed to relay any unanticipated problems/concerns/adverse events to the resident research coordinator ([name]). Data will be consolidated and sent to the resident researcher for further evaluation and for monitoring during the course of each patient's length of treatment.

The resident research coordinator ([name]) will ensure data accuracy by monthly asking how the data was collected and ensuring individuals are following proper protocol. In addition, data accuracy will also be maintained with quick training sessions on the study to be conducted at the study site once every 2 month basis. This will be done by the hand research coordinators/assistants, the resident researchers, or the principal investigators/attending involved. Monitoring work will be reviewed at regular intervals with the study Principal Investigator.

Patients that ultimately drop out of the study will be monitored for the course of their regularly scheduled follow-up appointments until there are discharged from the clinic or the care of the attending orthopaedic hand surgeon.

Primary and secondary efficacy endpoints will be monitored. Either patients will have resolution of their symptoms (primary endpoint) with improvement in hand function to their desired satisfaction or they must undergo surgery (secondary endpoint) for correction due to failure of the local soft tissue injection in relieving their symptoms.

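### The abandonment rule in section 3.4 names no direction, so a significantly lower failure rate on ketorolac would also end the study, with no efficacy boundary or reporting plan

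*Combined protocol and SAP*

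**What the plan says.** Section 3.4 starts from an expected ketorolac failure rate of 30-50%, which it takes from clinical experience and the literature on dexamethasone in trigger finger. It then says the study population will be "statistically analyzed biannually to determine if there is a significant difference in the rate of failures between the two groups". The consequence is mandatory: if the failure rate is "statistically significant between the ketorolac and dexamethasone group then the study will have to be ethically abandoned". Two qualifiers are attached. The first concerns size: "however a sizeable study population needs to be established before these conclusions can be drawn". The second concerns baseline severity: "This determination needs to take into consideration the pretreatment symptoms of the patient". Neither gives a direction.

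Section 2 sets the objective, which is to "compare local corticosteroid hand and elbow injections to ketorolac to determine if there is an equal or better reduction of symptoms".

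Section 7.1 sizes each disease group on mean DASH, and section 7.2 makes the quickDASH and EQ-5D scores the primary analysis. Section 3.4 does not define failure. The nearest wording is in section 10.1: patients either have their symptoms resolve "or they must undergo surgery (secondary endpoint) for correction due to failure of the local soft tissue injection". Sections 8.4 and 10.1 refer to a separate Data and Safety Monitoring Plan, which is not among the documents.

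**The concern.** The opening of the paragraph and its appeal to ethics suggest protection against an experimental drug that works worse than standard care. The operative sentence is wider. It is triggered by any significant difference, including one in which dexamethasone fails more often. A favourable finding on failure is within the stated objective, yet the protocol would treat it as grounds for abandoning the study.

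Two things are at stake. A trial stopped on an ordinary p<0.05 at an early look reports an exaggerated difference. It also stops before the functional-score comparison has its planned size. No efficacy boundary and no reporting plan cover such a stop. Whoever applies the rule must either follow the words or guess the intent.

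**Working it through.** **1. Does any text supply a direction?** The comparison and the consequence in 3.4 both speak only of a difference between the two groups. The size qualifier concerns when to look, and the severity qualifier concerns adjustment. No other section limits the rule to excess ketorolac failure or adds a rule for benefit. The point rests on this reading; the arithmetic below only shows whether the favourable trigger is remote.

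**2. The plan's own figure.** Section 7.1: difference 10, SD 25, effect size 0.4, alpha 0.05, power 80%.
- n per drug = 2(1.960 + 0.842)² / 0.4² = 98.1, so 99 per drug and 198 in total, against 200 stated.
- Power at 100 per drug = Φ(0.4√50 − 1.96) = Φ(0.868) = 0.807 (t-test 0.804).
- A one-sided calculation needs only 156, so the plan's 0.05 behaves as two-sided. I use two-sided 0.05 for the rule.

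**3. The rule as a test.** z = (p_D − p_K) / √(2p̄(1 − p̄)/n), with n per drug; abandon if |z| > 1.96. The look times are my assumption: 66, 130 and 196 patients of one disease with failure status known. The smallest observed difference that triggers the rule, with p̄ = 0.35, is 1.96√(0.455/n):
- n = 33: 23 points
- n = 65: 16 points
- n = 98: 13 points

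If the truth is 10 points, every stop at these looks therefore overstates it.

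**4. How often it fires in ketorolac's favour.** Simulation with binomial failures, unadjusted looks and no adjustment for severity. The last two schedules apply the 30% loss of section 7.1 to failure status as well.

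| Looks (status known) | 30% v 40%: abandoned in ketorolac's favour | Observed difference at that stop | Abandoned because ketorolac looks worse | 30% v 50%: abandoned in ketorolac's favour |
|---|---|---|---|---|
| 66, 130, 196 | 39% | 22 points | 0.3% | 85% |
| 130, 196 | about 35% | 19 points | 0.1% | 84% |
| 46, 92, 136 | 30% | 26 points | 0.5% | 71% |
| 92, 136 | 27% | 22 points | 0.2% | about 70% |

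In the first schedule with 30% v 40%, the mean stop is at about 125 patients with known status. If all diseases were pooled (looks at 196, 390 and 586), 30% v 40% would be abandoned in ketorolac's favour about 76% of the time.

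**5. What is left for quickDASH.** Power from a two-sample t-test, effect size 0.4, N evaluable patients; the normal approximation is Φ(0.4√(N/4) − 1.96).
- Full enrolment: 260 × 0.7 = 182 evaluable, 76.5% (approximation 77%).
- Stop at 125 patients who all have quickDASH data: 60%.
- Stop at 130 enrolled with 30% loss: 130 × 0.7 = 91 evaluable, 47%.

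**6. Does correcting for repeated looks cure it?** O'Brien-Fleming-type bounds for four looks (constant 2.024) put the three interim limits at |z| = 4.05, 2.86 and 2.34. For 30% v 40%, abandonment in ketorolac's favour falls from 39% to about 20%, at a mean of about 180 patients, or to 13.5% with loss applied. It falls but does not vanish, because the rule still has no direction.

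**The case against.** The strongest reply is that a two-directional ethical stop is a legitimate choice: if either drug clearly fails more often, including the standard of care, continued randomisation to it is an ethical question. That stands. A reader might infer that any early stop in ketorolac's favour is an error, and the documents do not support that. The defect is narrower: benefit and harm share one trigger and one consequence, at the ordinary significance level, with nothing on how a benefit stop would be reported.

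A reader might also infer that failure is merely a secondary matter that pre-empts the real endpoint. The documents conflict on this. Sections 3.2, 5.1.2 and 5.4 call resolution of symptoms or surgery the primary endpoint; sections 3.4, 4.4 and 10.1 label surgery secondary. On the first reading, a ketorolac advantage on failure would bear directly on the objective. Even then, an unplanned stop at p<0.05 gives an exaggerated estimate and leaves the sized comparison short.

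The unseen monitoring plan may state a direction. That cannot be checked, and section 3.4 would still have to agree with it.

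Finally, the protocol expects similar failure rates on the two drugs, and it leaves undefined how large a population must be before the rule applies. Both weaken any single percentage, though not the reading of the text.

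**Conclusion.** The point holds as a flaw in the wording of a mandatory rule: followed literally, it abandons the study for a result within its objective. It should be corrected.

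The size depends on assumed look times and true rates. For a 10-point advantage in one disease, 27-39% of trials would be abandoned in ketorolac's favour. For a 20-point advantage it is about 70-85%. A reader might infer that abandonment is the likely outcome whenever ketorolac is better. The figures do not support that for 10 points in one disease; it passes one half only with the larger gap or with pooled looks. Nor is 47% the quickDASH power at such a stop without qualification: it applies if 30% of about 130 enrolled patients are lost, and about 60% applies if some 125 patients have data.

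Repeated-look adjustment roughly halves the main figure and is a separate correction. The simulation leaves out the severity qualifier, and the minimum population for a look is assumed.

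**What to change.** State in section 3.4 that abandonment is triggered only by a failure rate significantly higher on ketorolac than on dexamethasone, and that a difference in ketorolac's favour at the ordinary 0.05 level does not end enrolment. In the 30% v 40% illustration, that leaves abandonment at 0.1-0.5%.

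If the sponsor wants to allow a stop for benefit, define it separately with a stringent, prespecified efficacy boundary and report it as an efficacy result, not as abandonment. Bring the Data and Safety Monitoring Plan into line, and reconcile the sections that disagree on whether surgery is a primary or a secondary endpoint.

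The core change is about one sentence in 3.4 and any matching text in the monitoring plan. The cost is small: if ketorolac is truly better, some further patients are randomised to dexamethasone, the standard of care.
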